7.4 Data Analysis and Reporting

Data analysis will be performed across all subjects based on Primary Analysis population unless otherwise specified.

The data collected will be presented using the appropriate summary statistics. Continuous data will be summarized using descriptive statistics (mean, number of observations, standard

deviation, minimum and/or maximum values) and categorical data will be summarized using frequencies and percentages.

7.4.2 The Secondary objectives

7.4.2.1 Safety Acute data

The major adverse cardiac events within 7 days post procedure will be summarized as a percentage of patients as defined

```
as: \frac{Number\ of\ subjects\ with\ major\ adverse\ cardiac\ events\ within\ 7\ days\ post\ procedure}{Number\ of\ subjects\ at\ baseline\ for\ that\ population}*100
```

 The peri-procedural events within 30 days post procedure will be summarized as a percentage of patients as described above.

7.4.2.2 Safety Midterm (6 months) and Long term (1-2 years) data

For all patients, the major adverse cardiac events will be recorded.

For patients undergoing the renal denervation procedure:

- The new renal artery stenosis (>50%) and/or aneurysm at the site of ablation per Renal Artery Imaging will be summarized at 6 and 12 months as percentage of patients who have stenosis and/or aneurysm. Image interpretation will be based on local analysis. Kaplanmeier analysis may be performed on the time to the first new renal artery stenosis and/or aneurysm at the site of ablation
- Renal function change based on eGFR will be summarized by:

- 1. Computing the change of the eGFR at 6 months, 12 months and 2 years compared to baseline for each patient with data available in both time points.
- 2. Calculating the mean and standard deviation of the eGFR change at those intervals

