3.2 Objectives

Primary Objective

To assess the feasibility of concomitant cardiac ablation for the treatment of atrial fibrillation and renal denervation ablation using the EnligHTN renal denervation system in achieving freedom from atrial fibrillation in patients with hypertension. Freedom from atrial fibrillation will be assessed based on electrocardiographic data during nine months following a blanking period of three months.

Secondary Objective

The secondary objectives are:

Safety

Acute:

Clinical Investigational Plan: RDN + AF

- The assessment of major adverse cardiac events (within 7 days post procedure)
- The assessment of peri-procedure events (within 30 days post procedure)

Midterm (6 months):

- Assessment of renovascular safety as measured by new renal artery stenosis or aneurysm at the site of ablation
- Renal function change based on eGFR (renal denervation group only)
- Assessment of major adverse cardiac events

Long term (12 months):

- Assessment of renovascular safety as measured by new renal artery stenosis or aneurysm at the site of ablation
- Renal function change based on eGFR (renal denervation group only)
- Assessment of major adverse cardiac events

AF Recurrence

 Recurrence of AF based on electrocardiographic data up to 2 years following the initial cardiac ablation procedure.

BP reduction

- Percentage of subjects achieving office Systolic Blood Pressure < 140 at 6 month visit
- Change in Office and Ambulatory Blood Pressure parameters at 12 and 24 months following the initial ablation procedure.

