4.1.10 Baseline Renal Artery Anatomy Evaluation

Adequate renal artery imaging is required to occur within 90 days prior to enrollment. Computed Tomography (CT) or Magnetic Resonance (MR) angiogram are recommended, non-contrast Magnetic Resonance Imaging (MRI) and doppler evaluation or ultrasound are acceptable. It is recommended that an MRI is performed to evaluate the renal artery anatomy to reduce the risk of radiation exposure.

Renal artery evaluation data collected will include but are not limited to:

- Type of evaluation computed axial tomography (CT scan), duplex ultrasonography, angiography, Doppler, magnetic resonance (MR) angiography, or non-contrast MRI
- Length of artery(s)
- Diameter of artery(s)
- Number of main renal arteries
- Number of accessory renal arteries
- Presence and percent of stenosis
- Other abnormalities

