4.5 Renal Denervation Procedure

For patients randomized to receive the renal denervation procedure, the procedure should be completed per the institution's standard of care and the study device Instructions for Use.

Procedural data collected will include but is not limited to:

- EnligHTN™ Renal Denervation System device information
- Guiding catheter used manufacturer
- Number of arteries ablated
- Number of ablations performed
- Device settings
- Procedure time
- Ablation time
- Fluoroscopic time
- Volume of contrast media

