5.12.2 Investigation Conclusion

The investigation will be concluded when:

- A Close Out visit has been performed at each participating center AND
- The Final report has been provided by the sponsor

6 Risks and Benefits of the Clinical Investigation

Anticipated Adverse Events and Adverse Device Effects

Possible adverse events associated with the cardiac ablation procedure include, but are not limited to:

Cardiac Events:

- Abnormal ECG
- Angina (chest pain)
- Arrhythmia
- AV fistula
- Complete heart block
- Coronary artery injury
- Cardiac Perforation
- Cardiac Thromboembolism
- Myocardial infarction
- Obstruction/perforation/damage of the vascular system

- Death
- Dislodgement of implantable cardioverter defibrillator permanent pacing lead
- Endocarditis
- Exacerbation of pre-existing atrial fibrillation
- Heart Failure
- Hypotension heart block)
- Left atrial / esophageal fistula
- Pulmonary vein dissection
- Pulmonary vein stenosis

SJM CONFIDENTIAL AND PROPRIETARY

- Palpitation
- Pericardial effusion/cardiac tamponade
- Pericardial effusion without tamponade
- Pericarditis
- CHF exacerbation fluid overload
- Component damage to ICD or implantable pacemaker

- Pulmonary vein thrombus
- Temporary or complete heart block
- Unintended (in)complete AV, sinus node, heart block/damage
- Vessel wall/valvular damage or insufficiency
- Ventricular arrhythmia requiring defibrillation
- Bradycardia

Non-Cardiac Events:

- Air embolism
- Anesthesia reaction
- Cerebrovascular accident
- High creatinine phosphokinase (CPK)
- Infections
- Local hematomas / ecchymosis
- Laceration
- Phrenic nerve damage
- Pneumonia

- Pulmonary edema
- Pulmonary embolism
- Pulmonary hypertension
- Pleural effusion
- Pseudoaneurysm
- Respiratory depression
- Skin burns
- Syncope
- Transient ischemic attack
- Vasovagal reactions
- Vasovagal episodes

- Pneumothorax
- Vasospasm

Possible adverse events associated with the renal denervation procedure include, but are not limited to:

- Acute renal injury (renal infarction, renal hematoma)
- Renal vascular injury (renal artery dissection, renal artery thrombosis, renal artery stenosis)
- Collateral tissue injury
- Malignant or accelerated hypertension
- Symptomatic hypotension
- Access site complications (arteriovenous fistula, access site thrombosis, embolisation, pseudo-aneurysm, hematoma, limb ischemia, femoral nerve injury, or seroma)
- Disseminated intravascular coagulation

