#### 2.5.2 Safety Midterm (6 months) and Long term (1-2 years) data

For all patients, the major adverse cardiac events will be recorded and summarized at 6 months, 1 year, and 2 years. Event rates will be calculated for each arm as the number of subjects who experienced a major adverse cardiac event over the number of subjects who experienced an event within or were followed to each time interval. Kaplan-Meier analysis may be performed for time to first major adverse cardiac event. For patients undergoing the renal denervation procedure:

The new (or worsened) renal artery stenosis (>50%) and/or aneurysm at the site of

- ablation per Renal Artery Imaging will be summarized at 6 and 12 months. A percentage of patients who have new stenosis and/or aneurysm compared to baseline will be provided. The denominator includes subjects with a baseline and follow-up assessment at the corresponding interval. Image interpretation will be based on local analysis. Kaplan-Meier analysis may be performed if applicable on the time to the first new renal artery stenosis and/or aneurysm at the site of ablation.
- Renal function change based on eGFR will be summarized by computing the change of the eGFR at 6 months, 12 months and 2 years compared to baseline (follow-up interval baseline) for each patient with data available in both time points. The mean and standard deviation of the eGFR change at those intervals will be presented.
- Overall renal vascular safety will be summarized as a rate of subjects with a serious, device or procedure related event over total subjects randomized to the renal denervation group at each follow-up time point.

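### The renal artery safety rate counts only lesions at an undefined ablation site, so its numerator is ambiguous and a silent new lesion elsewhere in a treated artery can fall outside it

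*Protocol*

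**What the plan says.** The objectives (Protocol 3.2, and the same in the synopsis) set out, at 6 and 12 months, "Assessment of renovascular safety as measured by new renal artery stenosis or aneurysm at the site of ablation". Protocol 7.4.2.2 turns this into a percentage of denervated patients with "new renal artery stenosis (>50%) and/or aneurysm at the site of ablation per Renal Artery Imaging", and allows a Kaplan-Meier analysis under the same limit. On reading, it says "Image interpretation will be based on local analysis".

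SAP 2.5.2 opens with the same limit, widened to new or worsened stenosis. Its next sentence, which states the percentage, speaks only of new stenosis or aneurysm relative to baseline and names no site. Its Kaplan-Meier sentence restores the limit: "time to the first new renal artery stenosis and/or aneurysm at the site of ablation". The SAP denominator is subjects with imaging at baseline and at the interval concerned.

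For the procedure, Protocol 4.5 lists "Number of arteries ablated" and "Number of ablations performed", along with device settings, times and contrast volume. For imaging, Protocol 4.1.10 lists artery length, diameter and number, "Presence and percent of stenosis", and other abnormalities. Protocol 4.10.9 lists the permitted modalities for follow-up imaging but no data items.

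**The concern.** A lesion enters the rate only if someone decides that it lies where energy was delivered. The plan gives no rule for that decision and does not require the data that would let anyone check it. Two analysts could also compute two different rates from the same records, depending on which SAP sentence they follow.

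The limit also cuts across the protocol's own view of the risk. Chapter 6 lists, among possible events of the denervation procedure, "Renal vascular injury (renal artery dissection, renal artery thrombosis, renal artery stenosis" with no restriction to the ablation points. A catheter passes along the artery as well as delivering energy at certain points in it. A new narrowing elsewhere in a treated artery is thus a plausible procedural harm, yet it can fall outside the rate by which renovascular safety is measured.

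**Working it through.** The plan has no expected rate, power calculation or interval for this endpoint, so there is no figure to reproduce. The check is of the text, followed by arithmetic for scale.

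**1. Is the numerator fixed?**

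| Source | Limited to the ablation site? | New only, or new and worsened? |
|---|---|---|
| Protocol objectives | yes | new |
| Protocol 7.4.2.2, percentage and Kaplan-Meier | yes | new |
| SAP 2.5.2, lead sentence | yes | new or worsened |
| SAP 2.5.2, percentage sentence | not stated | new |
| SAP 2.5.2, Kaplan-Meier sentence | yes | new |

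The SAP sentences do not define one quantity. The site term is not defined anywhere in the protocol or SAP.

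**2. Do the required data settle who counts?** The listed procedural items are counts of arteries and ablations. The listed imaging items give whether stenosis is present and how severe it is. Neither list names a position, so nothing in the plan requires the two locations to be recorded and compared.

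**3. Would another rate catch the lesion?** Take a silent stenosis above 50%, away from the ablation points, first seen at 6 months.

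- 30-day peri-procedural rate (Protocol 7.4.2.1, SAP 2.5.1): the window has closed.
- SAP overall renal vascular safety rate: it has no site limit, but the event must be serious or device or procedure related. The wording can also be read as requiring both seriousness and relatedness, which is narrower.
- Relatedness (Protocol 5.7.8): procedure related means that the event occurred during the procedure; device related means directly caused by the device. A late silent finding is not evidently the first, and is the second only if someone attributes it so.

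The lesion may be caught, but this is not assured.

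**4. Scale.** Inputs: the minimum of 50 denervated patients (Protocol 7.2, SAP 2.2), and 2/3 × 100 ≈ 67 from the protocol's upper enrolment figure. Both assume that every treated subject is imaged at both times. The exact (Clopper-Pearson) 95% upper bound is 1 − 0.025^(1/n) for no events and the 97.5th percentile of Beta(2, n − 1) for one event.

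| n | One lesion counted | Same lesion classed off-site |
|---|---|---|
| 50 | 1/50 = 2.0%, upper bound 10.6% | 0/50 = 0%, upper bound 7.1% |
| 67 | 1/67 = 1.5%, upper bound 8.0% | 0/67 = 0%, upper bound 5.4% |

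If fewer subjects are imaged, each lesion weighs more.

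**5. Could it arise?** The lesion rate is unknown. If it were 1%, 2% or 5% (assumptions), the chance of at least one lesion in 50 subjects, 1 − (1 − p)^50, is 40%, 64% or 92%.

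**The case against.** The strongest reply is that the plan may already hold what is needed. Both data lists are expressly not exhaustive, the imaging list has an item for other abnormalities, Appendix H says that the data points are supplied separately, and procedure notes are kept as source records. Protocol 7.4.3 and SAP 2.6 foresee results per kidney or per artery, which suggests more than simple counts. This stands. A reader might infer that position is not recorded, but the documents show only that the plan does not require it.

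A reader might also infer that off-site lesions escape safety reporting altogether. They need not. The SAP's overall rate has no site limit, adverse device effects are reportable whatever their severity, and serious or possibly related events are adjudicated internally (SAP 2.5.1). The sponsor's optional guiding catheter belongs to the study system, so damage that it directly causes would be device related. What remains is the silent lesion that nobody attributes.

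A third tempting reading is that the rate can only be biased downward. Compared with all new lesions in treated arteries that is true, because on-site lesions are a subset. For the endpoint as worded it is not: with no rule, a local reader could equally class an unrelated lesion as on-site. Nor is there a comparison between arms to distort, since follow-up imaging is confined to denervated subjects.

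Finally, the site limit has a purpose, which is to keep out disease unrelated to ablation. That is a reason to keep the on-site count, but not to make it the only count while it is undefined.

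**Conclusion.** The point holds as one of definition and coverage. The site limit is undefined, the SAP applies it inconsistently, and the plan does not require the data that would support it. A silent new stenosis or aneurysm elsewhere in a treated artery can therefore be left out of the rate that the objectives use to measure renovascular safety, and the other safety summaries are only a partial backstop.

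The numerical size is unknown because no lesion rate is given. The shift from one event to none shown above illustrates how much a single classification matters at this sample size; it is not an estimate of bias. The conclusion rests on the protocol and SAP text alone, and case report forms that record position would remove the data part of it but not the wording part. This is a descriptive secondary endpoint in a feasibility study with no hypothesis test. The change is worth making because it is cheap, not because the trial's main result depends on it.

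**What to change.** - In the synopsis and Protocol 3.2 objectives, in Protocol 7.4.2.2, and in the lead, percentage and Kaplan-Meier sentences of SAP 2.5.2, define one quantity: the percentage of subjects with any new or worsened stenosis above 50%, or aneurysm, in any renal artery that was ablated, main or accessory. Use the SAP's denominator of subjects with baseline and interval imaging throughout.
- Report lesions judged to be at the ablation site as a descriptive sub-line, with that term defined.
- Add artery, side and segment of each ablation to the items in Protocol 4.5, and the same for each lesion to the items in 4.1.10 and 4.10.9. First check whether the case report forms already hold them.

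No new imaging is needed. The cost is the rewording and, if the fields do not yet exist, a few additions to two forms. The downside is that a few lesions unrelated to ablation may be counted, so the rate may look slightly less favourable; the sub-line keeps the present quantity visible.

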7.4.2.3 AF Recurrence

The primary endpoint will evaluate recurrence of AF during the 9 months following the blanking period. Secondarily, the recurrence of AF based on electrocardiographic data at 3 months, 6 months and 24 months will also be reported.

Assessment of the AF recurrence will be determined through evaluation of 12 lead ECG recordings, holter monitoring or event recorder results. AF Recurrence is defined as episodes lasting longer than 30 seconds in duration. To count as a study-related recurrence, the AF episode must be documented. For this study, AF recurrence also includes (documented ≥30 seconds) atrial flutter and atrial tachycardia.

7.4.2.4 BP reduction

The mean reduction of office SBP at six (6) months of the study will be analyzed by:

- 1. Computing the reduction of SBP measurements at 6 months compared to baseline for each patient with data available in both time points.
- 2. Calculating the mean and standard deviation of the SBP reduction at 6 months

The data of

- Change in Ambulatory Blood Pressure parameters at 6 months,
- Change in Office Diastolic Blood Pressure at 6 months.
- Change in Office and Ambulatory Blood Pressure parameters

at 12 and 24 months post denervation will be calculated in the same way as described in the calculation of SBP reduction at 6 months.

 The percentage of subjects achieving office SBP < 140 at 6 months visit will be computed as follows:

 $\frac{\textit{Number of subjects achieving office SBP} < 140 \text{ at 6 months visit}}{\textit{Number of subjects with data available in 6 months visit}}*100$

7.4.3 Other Analyses

In addition, subgroup analyses may be performed as needed, e.g.:

- for subjects that have the renal denervation procedure performed on one side but not the other (due to their anatomy, circumstances related to the procedure, or physician judgment)
- based on the number of ablation points performed
- by the subject's primary disease conditions.

Ad hoc analyses may be performed as needed. Analysis may be performed based on As Treated population as appropriated. In general, data analysis will be performed on a per subject basis. But the data analysis may be presented per kidney, or on renal artery basis, as appropriate.

7.4.4 Analysis Software

The statistical analyses will be performed using SAS™ software version 9.2, or as specified and appropriate.

8 Data Management

All documents and data shall be produced and maintained in a way that assures control and traceability. Where relevant, the accuracy of translations shall be guaranteed and documented. All documents, and subsequent versions, related to a clinical investigation shall be identifiable, traceable and appropriately stored to provide a complete history of the clinical investigation.

eCRFs shall be developed by Sponsor to capture the data for each enrolled subject as required by the CIP. The eCRFs shall include information on the condition of each subject upon entering, and during the course of the clinical investigation, exposure to the device and any other therapies.

The Sponsor will be responsible for the data handling.

Data will be analyzed by the Sponsor and may be transferred to the Sponsor's locations worldwide and/or any other worldwide regulatory authorities in support of a market-approval application.

8.1 Data Management Plan

eCRF data will be entered by authorized investigative site personnel in a validated electronic database.

The Data Management Plan (DMP) describes all the computerized data cleaning checks (validation rules) as programmed at the time of database set-up. These validation rules may change and be updated throughout the course of the investigation.

Manual review and Data Cleaning Convention (DCC) will be used in addition to computerized data cleaning checks, to check for discrepancies and to ensure consistency of the data.

All revisions of the DMP will be tracked and include an effective date.

8.2 Source Documents

Source documents shall be maintained by the investigation site team throughout the clinical study. All findings in this clinical study must be documented as source data, and therefore can be verified (and audited). Source documentation may be paper or electronic, and is defined as the first time the data appears and may include for example; all clinical records, hospital records, surgery reports, autopsy reports, and any other material that contains original information used for clinical study data collection or adverse event reporting.

8.3 Source Data and Subject Files

The investigator shall keep written or electronic subject files for every subject participating in the clinical investigation. In this file, which will be kept on site, the available demographic and medical information of a subject shall be documented, in particular the following:

Name Age Weight

Clinical Investigation Plan - RDN+AF

Gender Height Concomitant Medication
Subject History Concomitant diseases Scheduled follow ups
PIC process Date of PIC Observed AEs
CIP required examination Clinical findings Procedure Notes

It should be possible to verify the inclusion and exclusion criteria for the investigation from the available data in this file. It must be possible to identify each subject by using this subject file. Additionally, any other documents with source data have to bear at least the subject identification and the printing date printed by the recording device to indicate to which subject and to which procedure the document belongs. The medical evaluation of such records should be documented as necessary and signed/dated by the investigator. All data recorded on the eCRF must be part of the subject's source data.

8.4 Confidentiality of Data

All subject information collected during the course of this study will be kept strictly confidential according to applicable country-specific laws and regulations. All data and information concerning subjects and their participation in this study are considered confidential by St. Jude Medical, Cardiology Division, Inc., d/b/a St. Jude Medical, Cardiovascular Division, Inc., a U.S. company, and its affiliates (located in the U.S.A. and European Economic Area (EEA), Canada, and other countries), and other people who work for SJM to provide services related to the device and this study (collectively referred to as "SJM"). All public reporting of the results of the study will eliminate identifiable references to the subjects. Information on paper will be kept in secured locations. Electronic information will be kept on password-protected computers.

Personal data, including medical and health information, will be processed both by computer and manually, during and after the study by SJM, and its affiliates, its designated third party data processors, the EC, the institution conducting the study, the study doctors and other healthcare personnel involved in the study for the purposes of this study. The electronic data stored for this study will be kept in an SJM database, in compliance with applicable law. Subject data will not contain details of study subject identity. The data will be stored on a secure server and backed up routinely. Personal data will be key-coded to prevent subject identification, except by the institution, study doctors and other healthcare personnel involved in the study, if necessary for the purpose of the study, for regulatory inspections, and to comply with SJM reporting obligations.

Study subjects have a right to gain access and to correct inaccuracies in information about them as permitted by applicable law.

In order to help keep subject medical records and personal information confidential only certain authorized investigators and SJM personnel, or approved contracted agents of SJM, will have access to confidential records. These include researchers in the hospital who are part of this study, SJM and its affiliates and representatives that perform study-related services who may be located in the U.S.A., Canada, European Economic Area (EEA) and other countries. The Ethics Committee (EC) and other regulatory authorities also have the right to inspect and copy records pertinent to this study. It is necessary for them to review study data, portions of study subject records and information so that they can follow the study progress, which may include without limitation:

- Monitor the accuracy and completeness of the study
- Perform scientific analysis and develop the medical product
- And/or obtain approval to market the medical products in the USA, Canada, EEA, and other countries.

Any information about subjects that leaves the institution conducting the study will be modified to remove certain information that could identify the subject (e.g., subject's name, age on the day of enrollment, address, and hospital number) and only be identifiable by a study specific subject ID code. Study data provided to SJM that is published in medical journals and/or presented at scientific conferences will not allow the identification of study subjects.

The results of the study will be made available to SJM and its affiliates (located in the U.S.A., EEA, Canada, and other countries) and other people who work for SJM to provide services related to the device and this study and study center.

A summary of the information on all subjects may be provided to governmental agencies (including regulatory agencies), regulatory authorities in the U.S.A., Canada, EEA and other countries who may also need to review study data and portions of medical records. Results from this study may also be published in scientific journals or presented at conferences as an oral or poster presentation; however, the identity of a study subject will not be disclosed.

9 Document Retention

The Principal Investigator (PI) shall maintain all essential clinical investigation documents from prior, during and (as specified) after the clinical investigation on file at the site for a minimum of 15 years after the termination of this investigation, or longer as per local laws, or when it is no longer needed to support a marketing application, whichever is later.

The PI must contact the sponsor prior to destroying or archiving off-site any records and reports pertaining to this investigation to ensure that they no longer need to be retained on-site.

All original subject files must be stored for the longest possible time permitted by the regulations at the hospital, research institute, or practice in question. If archiving can no longer be maintained at the site, the investigator will notify the sponsor.

All data and documents shall be made available on request of the relevant authorities in case of an audit.

The sponsor will archive and retain all essential clinical investigation documents from prior, during and (as specified) after the clinical investigation as per requirements.

10 Amendments to the Clinical Investigational Plan

The CIP, eCRFs, Patient Informed Consent form and other subject information, or other clinical investigation documents shall be amended as needed throughout the clinical investigation, and a justification statement shall be included with each amended section of a document. Proposed amendments to the CIP shall be agreed upon between the Sponsor and Principal Investigator, or the Coordinating Investigator.

The amendments to the CIP and the Patient Informed Consent shall be notified to, or approved by, the EC and regulatory authorities, if required. The version number and date of amendments shall be documented.

The amendment will identify the changes made, the reason for the changes and if it is mandatory or optional to implement the amendment.

Any amendment affecting the subject requires that the subject be informed of the changes and a new Patient Informed Consent be signed and dated by the investigator and subject prior to the subject's next follow up.

Changes to, or formal clarifications of, the CIP will be documented in writing and provided to the investigators by the Sponsor. This information will be incorporated by the Sponsor when an amendment occurs.

11 Publication Policy

A 'Publication Agreement' will be signed between the Principal Investigator and the Sponsor (if applicable).

If such a Publication Agreement is not signed by both parties as a separate agreement but as part of an overall Clinical Trial Agreement, the publication policy should be part of the Clinical Trial Agreement.

For more information on publication guidelines, please refer to the International Committee of Medical Journal Editors (ICMJE) on www.icmje.org.

12 Investigation Organization

